3.2 General study level definitions

3.2.1 Analysis time points

The study includes 3 periods as follows:

- **Period 1** (Screening Period): 1 to 5 weeks before Baseline

The pre-treatment period (Screening period) of the study is the period prior to a subject's first dose of study medication intake. This period starts at the Screening visit (week -5 to -1 day, extended to week -12 for subjects who start a prophylactic treatment for LTBI) and ends at the Baseline visit (Week 0) up to the time of first study medication administration (exclusive). Unless specific time information is available to indicate that a Screening or Baseline visit assessment was performed after a subject's first study medication administration, most assessments will be attributed to the Screening period. Exceptions to this are AEs that start on Baseline visit, as they will be attributed to the Treatment Period.

- **Period 2** (Treatment Period): Week 0 to Week 96

The treatment period begins at the Baseline visit (Week 0) at the time of first study medication administration (inclusive) and ends at Week 96/WD visit. Premature withdrawal visit assessments will be assigned to the next scheduled visit following the last visit where assessments are available. All visit measurements, even violating the visit window, will be utilized for the respective visit as long as they are in the proper sequence. Subjects will be classified as completing the study if they complete the Week 96 Visit without early withdrawal of the study. This is regardless of whether they attend the Follow-up visit.

- **Period 3** (FU Period): 10 weeks from the final dose of study medication received

The Follow-up visit will take place 10 weeks after the last dose of study medication. That is either 8 weeks after the Week 96 visit for subjects completing the study, or up to 10 weeks after the WD visit for withdrawn subjects.

3.2.2 Relative day

The relative day will be included in different listings and will be calculated as follows:

- If the start (stop) date occurred on or after the first dose, but prior to the drug stop date, relative day is calculated as start (stop) date minus first dose date + 1.
- If the start (stop) date occurred after the last dose of drug, the relative day to the most recent dose is calculated as start (stop) date minus most recent dose date. The relative day in this situation should be preceded by a '+'.

- If the start (stop) date occurred before the first dose, the relative day is calculated as start (stop) date minus first dose date. The relative day in this situation should be preceded by a '-'.
'-'.

For AEs, relative days for start and stop dates will be calculated as the number of days since the first injection of the medication. For non-treatment emergent AEs, relative day of onset will be negative if the event started and stopped before the first dose. Relative day will only be computed for fully completed dates and will be missing for partial dates.

3.3 Definition of Baseline values

Unless otherwise specified, the last valid measurement before study medication administration will be utilized as Baseline value. For almost all variables, this will be the assessment made at the Baseline visit. However, for some variables, assessments may be scheduled for Screening only and not for Baseline. In this case the screening value will be utilized as baseline value. If a baseline measurement is missing, and a screening value available, the screening value will be utilized as Baseline instead. If a scheduled Baseline assessment is taken on the same day as first administration of study medication, it will be used as Baseline, irrespective of the time of the assessment relative to the first administration of study medication.

3.4 Protocol deviations

Important protocol deviations (IPD) are deviations from the protocol which could potentially have a meaningful impact on study conduct, on the safety for an individual subject, or on the primary efficacy outcome for an individual subject. The criteria for identifying important protocol deviations will be defined within the specification of the IPD document. Important protocol deviations will be reviewed as part of the ongoing data cleaning process and all important deviations will be identified and documented prior to database lock.

Important protocol deviations will be identified and classified by the deviation types defined in the IPD document. A listing of all important protocol deviations identified at the Data Evaluation Meeting will be presented for all subjects in the SS, and will include deviation type and description. The number and percentage of subjects in the SS with important protocol deviations will be summarized overall.

The following deviation types, and further deviation types, may be included in the IPD:

- Inclusion criteria
- Exclusion criteria
- Withdrawal criteria
- Exposure
- Non-compliance
- Prohibited concomitant medications

3.5 Analysis sets

The main analysis sets defined for this study are the Enrolled Set (ES) and the Safety Set (SS). In addition, a Full Analysis Set (FAS) is defined for the unexpected case of missing Baseline values

for the primary efficacy variable. A Per Protocol Set (PPS) is added for additional analysis of the primary efficacy variable only.

3.5.1 Enrolled Set

The ES will consist of all subjects who have given informed consent.

3.5.2 Safety Set

The SS will consist of all subjects in the ES who have received at least 1 dose of study medication.

Safety variables, and also efficacy variables, will be summarized using the SS.

3.5.3 Full Analysis Set

The FAS will consist of all subjects in the SS with non-missing Baseline value for the primary efficacy variable, i.e. AU flare incidence data from pre-study period.

In case the FAS differs from the SS, the efficacy analysis will be conducted using the FAS instead of the SS.

3.5.4 Per Protocol Set

The PPS will consist of all subjects in the SS, or in the FAS if applicable, which do not have any important protocol deviation affecting the primary efficacy variable. Subjects with at least one important protocol deviation affecting the primary efficacy variable will be excluded from the PPS.

3.6 Treatment assignment and treatment groups

At Baseline, eligible subjects will be assigned to the study treatment CZP. Certolizumab pegol will be administered as 400mg at Baseline and Weeks 2 and 4 followed by 200mg Q2W (starting at Week 6 until Week 94). As there is a single treatment arm in this study, all subjects will be presented together in a single treatment group (eg, as “CZP”). For presentation purposes, the term CZP will be used.

3.7 Center pooling strategy

All results will be summarized across centers and will not be stratified by center. No pooling of centers is planned for this study.

3.8 Coding dictionaries

All AEs, concomitant diseases, and medical history will be coded for analysis according to the Medical Dictionary for Regulatory Activities (MedDRA)[®] coding dictionary, version 19.0. Prior and concomitant medications will be coded for analysis using the World Health Organization Drug dictionary (WHO-DD), version SEP/2015.

3.9 Changes to protocol-defined analyses

The analysis of Axial SpondyloArthritis international Society response ASAS5/6 will not be performed as described in the clinical study protocol, because one main component for spinal mobility, the Bath Ankylosing Spondylitis Metrology Index (BASMI), is not collected in the data.

The ASAS 5/6 response is defined as at least 20% improvement in 5 of the following 6 domains:

- Patient's Global Assessment of Disease Activity
- Pain assessment (the total spinal pain NRS score)
- Function (represented by the Bath Ankylosing Spondylitis Functional Index (BASFI))
- Inflammation (the mean of the Bath Ankylosing Spondylitis Disease Activity Index (BASDAI) questions 5 and 6) [REDACTED]
- Spinal mobility (lateral lumbar flexion measured by BASMI)
- CRP as more objective measures

As the BASMI is not collected, and there is no alternative measure of spinal mobility available in the study data, the complete component for spinal mobility is missing. Therefore the ASAS 5/6 response criterion cannot be calculated, and the analysis of the secondary efficacy variable ASAS 5/6 has to be dropped.

The clinical study protocol does not mention a PPS. This analysis set has been added, in order to additionally perform the primary efficacy analysis on the subset of protocol-compliant subjects.

In the calculation of ASDAS (Section 9.1.2 of the protocol), the CRP component was written as " $0.579 \times (\text{natural logarithm of the CRP [mg/L]} + 1)$ ", but should have been " $0.579 \times (\text{natural logarithm of the (CRP [mg/L]} + 1))$ ".

For BASDAI (Section 9.1.3 of the protocol), the protocol stated "The BASDAI is a validated self-reported instrument which consists of six 10-unit horizontal NRSs to [REDACTED]

[REDACTED] over the last week". However the severity and duration are only measured for [REDACTED], the others are measured for severity only.

In Section 9.1.4 of the protocol, the pain assessment component of ASAS20/40/PR was defined as "the average of total and nocturnal spinal pain NRS scores", but this should be defined as total spinal pain NRS score only.

ASDAS Clinical improvement was detailed as an "other" efficacy variable, but no definition was given. As there is no well-accepted definition, this variable has not been included in the analysis.

In Section 12.7 of the protocol, it stated that the interim analysis would use $\alpha=0.0001$ and so the final analysis would use $\alpha=0.049$. This should have said that $\alpha=0.001$ would be used for the interim analysis.

4 STATISTICAL/ANALYTICAL ISSUES

4.1 Adjustments for covariates

Statistical models may be adjusted for covariates. Any such adjustments will be described in the context of the analyses to be performed.

4.2 Handling of dropouts or missing data

Analysis is based on observed case only.

If the Baseline value is missing, the Screening value may be used as the Baseline. In general, if no measurement is available prior to receiving study medication, then the Baseline value is treated as missing, and will not be imputed.

Premature withdrawal visits should be assigned to what would have been the next scheduled visit for the particular assessment that is being summarized. If a premature withdrawal visit occurs on the same date as a scheduled visit, then the assessments will be summarized with the scheduled visit.

Safety variables

For analyses of AEs and concomitant medication usage, a complete date must be established in order to correctly identify the AE or medication as occurring during treatment or not. For purposes of imputing missing components of partially-reported start and stop dates for AEs and for medication use, the algorithms listed below will be followed. Start and stop dates of AEs or concomitant medication will be displayed as reported in the subject data listings (i.e., no imputed values will be displayed in data listings).

- Missing start day, but month and year present: If the start of study medication occurred in the same month and year as the occurrence of the AE/concomitant medication, the start day of the event/concomitant medication will be assigned to the day of first intake of study medication. Otherwise the start day will be set to the 1st day of the month.
- Missing start day and month, but year present: If the start of study medication occurred in the same year as the occurrence of the AE/concomitant medication, the start day and month will be assigned to the date of first intake of study medication. Otherwise the start day and month will be set to January 1st.
- If start day, month, and year are missing, start date will be replaced by the date of first study drug administration or by the first day of January of the year of the end date, if the first administration date is after the end date.
- Missing end day, but month and year present: The end day will be set to the last day of the month.
- Missing end day and month, but year present: If the maximum of the subject's date of study termination or the date equivalent to 70 days after the subject's last intake of study medication is the same year as the occurrence of the AE/Concomitant medication, then the end day and month will be set to the maximum of the date of study termination or the date equivalent to 70 days after last intake of study medication. Otherwise the end day will be set to December 31st of the given year.

Efficacy variables

The start and end dates of flares will be imputed for the analyses of AU flares data, in order to allow the calculation of time intervals between 2 consecutive flares and the duration of flares. Different rules will be applied for pre-study and on-study period flares.

For the interim analysis, the pre-study period is starting 48 weeks prior to Baseline, i.e. 336 days prior to Baseline until Baseline. The on-study period for the interim analysis is starting from Baseline until week 48, i.e. until study day 336.

For the final analysis, the pre-study period is starting 24 months prior to Baseline, i.e. 730 days prior to Baseline until Baseline. The on-study period for the final analysis is starting from Baseline until week 96, i.e. until the date of the Week 96 or discontinuation visit. In addition, sensitivity and supportive analyses use different definitions (as defined in Section 8.1.2).

Pre-study period:

- Missing start day, but month and year present: Impute the first day of the month unless one of the following conditions apply:
 - Month and year are the same as month and year of the start date of pre-study period, then impute with the start date of pre-study period.
 - Month and year are the same as month and year of the end date of previous flare in the same eye, and the end date is clearly greater than end date of previous flare, then impute with the end date of previous flare.
 - In the case that month and year of the start date of pre-study period is the same month and year of the end date of previous flare in the same eye, then use the latest date of both for imputation.
- Missing start day and month, but year present: Impute January 1st unless one of the following conditions apply:
 - Year is the same as year of the start date of pre-study period, then impute with the start date of pre-study period.
 - Year is the same as year of the end date of previous flare in the same eye, then impute with the end date of previous flare.
 - In the case that year of the start date of pre-study period is the same year of the end date of previous flare in the same eye, then use the latest date of both for imputation.
- Completely missing start dates of flares will only be imputed if it is clear based on the end date that the flare occurred within the pre-study period. Then the maximum (latest) of start date of pre-study period and end date of previous flare will be considered.
- Missing end day, but month and year present: Impute the last day of the month unless one of the following conditions apply:
 - Month and year are the same as month and year of the end date of pre-study period, then impute with the end date of pre-study period.
 - Month and year are the same as month and year of the start date of subsequent pre-study flare in the same eye before Baseline, then impute with the start date of subsequent pre-study flare.
 - In the case that month and year of the end date of pre-study period is the same month and year of the start date of subsequent pre-study flare in the same eye, then use the earliest date of both for imputation.
- Missing end day and month, but year present: Impute December 31st unless one of the following conditions apply:

- Year is the same as year of the end date of pre-study period, then impute with the end date of pre-study period.
- Year is the same as year of the start date of subsequent pre-study flare in the same eye, then impute with the start date of subsequent pre-study flare.
- In the case that year of the end date of pre-study period is the same year of the start date of subsequent pre-study flare in the same eye, then use the earliest date of both for imputation.
- Completely missing end dates of flares will only be imputed if it is clear based on the start date that the flare occurred within the pre-study period (of 2 years prior to baseline). Then the minimum (earliest) of end date of pre-study period (i.e. the day prior to treatment start date), the day prior to start date of subsequent pre-study flare in the same eye, or the start date plus the median duration of flare in that subject will be considered. The median duration of flare is determined from all flares recorded for that subject that have complete start and end dates (regardless of eye), including any flares prior to or during the pre-study period and on-study period.

On-study period (Baseline until end of treatment):

- Missing start day, but month and year present: Impute the first day of the month unless one of the following conditions apply:
 - Month and year are the same as month and year of the start date of study medication, then impute with the start date of study medication.
 - Month and year are the same as month and year of the end date of previous on-study flare in the same eye, and the end date is clearly greater than end date of previous on-study flare in the same eye, then impute with the end date of previous on-study flare in the same eye.
 - In the case that month and year of the start date of study medication is the same month and year of the end date of previous on-study flare in the same eye, then use the latest date of both for imputation.
- Missing start day and month, but year present: Impute January 1st unless one of the following conditions apply:
 - Year is the same as year of the start date of study medication, then impute with the start date of study medication.
 - Year is the same as year of the end date of previous on-study flare in the same eye, then impute with the end date of previous on-study flare in the same eye.
 - In the case that year of the start date of study medication is the same year of the end date of previous on-study flare in the same eye, then use the latest date of both for imputation.
- Completely missing start dates of flares will only be imputed if it is clear based on the end date that the flare occurred after treatment start during the on-study period. Then the maximum (latest) of start date of study medication and end date of previous on-study flare in the same eye will be considered.

- Missing end day, but month and year present: Impute the last day of the month unless one of the following conditions apply:
 - Month and year are the same as month and year of the end date of on-study period, then impute with the end date of on-study period.
 - Month and year are the same as month and year of the start date of subsequent on-study flare in the same eye, then impute with the start date of subsequent on-study flare in the same eye.
 - In the case that month and year of the end date of on-study period is the same month and year of the start date of subsequent on-study flare in the same eye, then use the earliest date of both for imputation.
- Missing end day and month, but year present: Impute December 31st unless one of the following conditions apply:
 - Year is the same as year of the end date of on-study period, then impute with the end date of on-study period.
 - Year is the same as year of the start date of subsequent on-study flare in the same eye, then impute with the start date of subsequent on-study flare in the same eye.
 - In the case that year of the end date of on-study period is the same year of the start date of subsequent on-study flare in the same eye, then use the earliest date of both for imputation.
- Completely missing end dates of flares will only be imputed if it is clear based on the start date that the flare occurred after treatment start during the on-study period. Then the start date of subsequent on-study flare in the same eye will be considered. Otherwise it will be assumed to be ongoing.

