5.1.1 Study duration per subject

For each subject, the study will last a maximum of 109 weeks, as follows:

- Up to 5 weeks of Screening Period (see Section 10.6.4.1 for details on an extended Screening Period of 12 weeks)
- A Treatment Period of 96 weeks
- A FU Visit at Week 104

The end of the study is defined as the date of the last study FUV isit.

Planned number of subjects and sites 5.1.2

Approximately 130 subjects will be screened in order to enroll 86 subjects into the study.

The estimated recruitment period will be approximately 12 months. This takes into account an estimate of a 35% screen failure rate between Screening and Baseline. Prematurely discontinued randomized subjects will not be replaced.

Subjects are planned for enrollment at approximately 20 to 30 sites.

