2.2.1.2 Secondary efficacy variables

The following secondary efficacy variables will be assessed at Week 48 and Week 96:

- Number of AU flares per 100 patient-years in subjects with active axSpA and a history of AU
- Number of AU flares per 100 patient-years in subjects with active axSpA and at least 1 AU episode within 12 months prior Baseline
- Change from Baseline in Ankylosing Spondylitis Disease Activity Score (ASDAS)
- Change from Baseline in Bath Ankylosing Spondylitis Disease Activity Index (BASDAI)
- Assessment of ASAS 20, 40, 5/6, and partial remission (PR) response rates
- Change from Baseline in tender and swollen joint count (44 joint count); Physician's Global Assessment of Disease Activity (PhGADA).
- Change from Baseline in the respective components of the ASAS response criteria, assessed by:
 - Patient's Global Assessment of Disease Activity (PtGADA)
 - Pain assessment (total spinal pain Numerical Rating Scale [NRS])
 - Function (represented by Bath Ankylosing Spondylitis Functional Index [BASFI])
 - Inflammation (the mean of the BASDAI questions 5 and 6 concerning [REDACTED])

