2.4 Determination of sample size

Based on results from a previous study with CZP in axSpA subjects (AS001), the AU flare rate while treated with CZP is estimated to be 14.6 events per 100 subject-years of exposure. Assuming the rate while treated with CZP represents a reduction in the flare rate of approximately 50%, the AU flare rate for the prestudy period prior to initiation of CZP is estimated to be 29.2 events per 100 subject-years of exposure. A conservative estimate of the sample size for this study is obtained via derivation of the per treatment-group sample size for Poisson regression based on the approach for a 2-group setting initially described by Signorini (1991) and implemented within SAS (Hu, 2008). Assuming an average follow-up period of 1.5 years with 2-sided α -level=0.049 for the final analysis of the primary efficacy variable, a sample size of N=86 subjects per treatment group will have 80% statistical power for a 2 group comparison, corresponding to a total sample size of N=86 subjects for this study with 1 treatment group. Due to the expected increase in statistical efficiency from the fact that each subject serves as his/her own control in the primary efficacy analysis, the actual power for this study is assumed to be >80 percent.

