Unless stated otherwise, all inferential statistical tests will be 2-sided and conducted at the 0.05 alpha level. Adjustment for multiplicity is described in [Section 4.5](#). P-values for secondary efficacy variables are nominal. P-values will be presented to 3 decimal places and any values below 0.001 should be displayed as “<0.001”.

All data in the database (SDTM and ADaM) will be presented in by-subject data listings, and sorted by subject number, parameter (where applicable), and visit (where applicable). For listings including subjects that were not treated, these subjects will be shown first in the listing, ordered by subject number. All listings will include repeated and unscheduled measurements. Such measurements will appear in chronological order together with the scheduled visits, i.e., a repeated measurement will appear directly after the visit and time relative to dosing, for which the repeat measurement was performed. In all the listings dates will be presented in the format ‘YYYY-MM-DD’ and times will be presented in 24h clock format as ‘hh:mm’ or ‘hh:mm:ss’ where appropriate.

All tabulations will be sorted by parameter and visit. Only scheduled visits will be included in the tabulation. Categorical data will be summarized by visit, using the number and percentage of subjects in each category. Percentages will be based on the corresponding population size (i.e., the denominator of percentages should match the sample size in the column header), unless otherwise noted via footnote in the applicable summary table. Percentages will be presented to 1 decimal place. For data points with $n=0$ (i.e., no subjects in the applicable category), no value for percentage of subjects will be displayed.

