8.2 Statistical analysis of the secondary efficacy variable(s)

Secondary and other efficacy variables will be summarized by time point including change from Baseline or shift from Baseline, with descriptive statistics. Arithmetic mean, SD, median, minimum and maximum value will be displayed for continuous variables. The secondary efficacy variables are assessed at Week 48 and Week 96. All efficacy analyses will be based on the SS or FAS as appropriate.

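### Continuous axSpA outcomes at Week 48 and Week 96 rest on observed cases with no missing-data sensitivity analysis, so improvement can be overstated

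*SAP*

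**What the plan says.** The disease-activity part of the secondary objectives is answered at two time points: "The following secondary efficacy variables will be assessed at Week 48 and Week 96" (SAP 2.2.1.2). The missing-data rule in SAP 4.2 is "Analysis is based on observed case only". SAP 8.2 adds: "Secondary and other efficacy variables will be summarized by time point including change from Baseline or shift from Baseline, with descriptive statistics". The supportive and sensitivity analyses in SAP 8.1.2 concern flares only.

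The item-level rules are narrow. SAP 8.2.2 carries forward one missing ASDAS component, but a wholly missed visit leaves the score missing. Under SAP 3.2.1 and 4.2, an early-withdrawal visit is mapped to the next visit in the schedule and no further.

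On who leaves, Protocol 6.3 lets the investigator withdraw a subject so that another therapy can be given. Protocol 7.8.2 requires withdrawal before a prohibited drug, including another TNF antagonist, is started.

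For categorical outcomes, SAP 3.1 bases percentages on the analysis set, includes a row for missing values, and says that "the denominator of percentages should match the sample size in the column header" unless a footnote states otherwise. SAP 8.2.4 gives no denominator for ASAS20, ASAS40 or partial remission.

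**The concern.** A subject who does badly and leaves at, say, Week 26 contributes to the Week 32 or Week 36 summary and then disappears. The Week 48 and Week 96 means are taken over those still attending. If staying is related to doing well, the mean change among stayers is larger than the mean change in everyone treated. With a single arm, no between-group comparison could show that this has happened, and no planned analysis of these measures tests how far the result depends on it.

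At stake is the size of the reported improvement in ASDAS, BASDAI, BASFI, PtGADA and spinal pain, which is what answers a named secondary objective.

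**Working it through.** **Inputs**
- Treatment length: "A Treatment Period of 96 weeks" (Protocol 5.1.1). 96 × 7 / 365.25 = 1.840 years; Week 48 is 0.920 years.
- Planning follow-up: "Assuming an average follow-up period of 1.5 years" (SAP 2.4).
- Planning rates: 0.292 and 0.146 flares per subject-year (SAP 2.4).
- On-study dropout rate: none stated. The 35% in Protocol 5.1.2 is screen failure before Baseline.
- The text of Protocol 12.6 on dropouts was not legible in the copy reviewed, so nothing is inferred from it.

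**The plan's own figure.** SAP 2.4 states "a sample size of N=86 subjects per treatment group will have 80% statistical power", "with 2-sided α -level=0.049 for the final analysis". The Signorini formula with two equal groups gives

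N total = [z(0.9755) × √4 + z(0.80) × √(2 + 2/0.5)]² / (1.5 × 0.292 × (ln 0.5)²) = 171.0,

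or 85.5 per group, rounded up to 86. So 1.5 years is the exposure per subject used in both groups of the formula.

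**Dropout if 1.5 years is read as mean on-study follow-up (assumption)**
- Floor, all leaving at Week 0: 1 − 1.5/1.840 = 18.5%.
- All leaving at Week 24: (1.840 − 1.5) / (1.840 − 0.460) = 24.6%.
- Constant hazard: (1 − e^(−1.840h)) / h = 1.5 gives h = 0.230 per year. Gone by Week 96: 1 − e^(−0.230 × 1.840) = 34.5%. Gone by Week 48: 1 − e^(−0.230 × 0.920) = 19.1%.
- Uniform over 96 weeks: 2 × (1 − 1.5/1.840) = 36.9%.
- All leaving at Week 72: 73.9%.

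Under constant hazard about 70 of 86 subjects are observed at Week 48 (86 × 0.809) and about 56 at Week 96 (86 × 0.655). The average alone sets a minimum for Week 96 but none for Week 48, because all losses could fall after it.

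**Bias in an observed-case mean.** With d the fraction gone, bias = d × (stayer mean − leaver mean). For each 1-unit gap that is 0.18 unit at the floor, 0.35 under constant hazard and 0.37 under uniform dropout.

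If leavers improve half as much as stayers (assumption), observed-case mean ÷ all-subject mean = 1 / (1 − d + 0.5d):
- Week 96, d = 0.185: 1 / (0.815 + 0.0925) = 1.10.
- Week 96, d = 0.345: 1 / (0.655 + 0.1725) = 1.21.
- Week 96, d = 0.369: 1 / (0.631 + 0.1845) = 1.23.
- Week 48, d = 0.191: 1 / (0.809 + 0.0955) = 1.11.

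**Responder rates.** Suppose 50% of those observed respond. On the full analysis set the rate is 0.50 × 0.655 = 33% (constant hazard) or 0.50 × 0.631 = 32% (uniform). The gap between the two denominators is therefore large, but which of them the SAP means is a question of wording, taken up below.

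**The case against.** The strongest reply is that the documents forecast no dropout. The 1.5 years is a sample-size input that the SAP calls conservative, and it serves both groups of the formula, including the historical period, from which nobody can drop out. A reader might infer that the plan expects about a third of subjects to be lost by Week 96. It does not say so: 34.5% needs the added assumption of constant hazard, and only the 18.5% floor follows once 1.5 years is read as on-study follow-up. This stands, and the figures above are conditional for that reason.

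A reader might also infer that ASAS and other response rates will be inflated, with a reported 50% concealing 32%. SAP 3.1 points the other way. An analysis-set denominator with a missing row has the same numerical effect as counting missing as non-response, and the 4.2 rule can be read as meaning only that values are not imputed. This also largely stands. What remains is that 3.1 and 4.2 are not tied together for these endpoints.

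Selection for response is possible, not shown. Changing therapy is one of several routes out, and rescue medication is allowed through Week 96 (Protocol 7.8.3), so poor response need not lead to withdrawal. Attrition will also be visible: n per visit, the reasons for discontinuation and a full set of withdrawal assessments are all planned. Visibility, however, does not correct a mean or show how sensitive it is.

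**Conclusion.** The point holds for the continuous axSpA measures: they are summarised on those still attending, without any check on missing data, and response-related withdrawal would push improvement upwards. Under the stated assumptions the overstatement at Week 96 is about 10% at the floor, 21% under constant hazard and 23% under uniform dropout; at Week 48 it is about 11% under constant hazard. A smaller difference between leavers and stayers would shrink these figures, and no difference would remove them.

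Two wider conclusions would go too far. First, the flare results are outside this point. The primary model and the rates per 100 patient-years use each subject's own time on study, so leavers still contribute their events and time. Second, the illustration inflates a real within-subject change; it does not suggest that the change is produced by dropout.

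SAP 8 makes everything except the primary analysis exploratory. This is a worthwhile improvement to a secondary objective, not a threat to the confirmatory test.

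**What to change.** 1. Keep the observed-case summaries, with n shown at each visit. For each continuous measure add a mixed model for repeated measures on all scheduled visits, with visit as a factor. Report Week 48 and Week 96 mean changes with 95% confidence intervals, and state the missing-at-random assumption. Pre-specify one covariance structure and a named fallback. With 10 or 11 post-Baseline visits an unstructured matrix has 55 (10 × 11 / 2) or 66 (11 × 12 / 2) parameters for 86 subjects, so it may not converge.
2. Reconcile SAP 3.1 and 4.2 in one sentence: ASAS20, ASAS40, partial remission, BASDAI50 and the ASDAS response rates are responders divided by all Safety Set subjects, with missing counted as non-response and the observed-case rate shown beside it.

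No new data are needed; the withdrawal-visit assessments already required give the model each leaver's last status. The cost is one extra model per variable, reliance on missing at random, and possibly slightly less favourable figures.
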